#### 19.4. Primary Analyses

The primary objective is to determine the therapeutic efficacy (as measured by response rate) of abatacept + ixazomib + dexamethasone in multiple myeloma patients who have relapsed after treatment with their first proteasome inhibitor-containing regimen (excluding ixazomib) and have not been treated with a second proteasome inhibitor.

Previous studies have demonstrated a response rate of approximately 30% for ixazomib + dexamethasone as second line therapy in this patient population (34). We hypothesize that the proposed treatment combination (abatacept + ixazomib + dexamethasone) will improve the second-line response rate in this patient population. Therefore, we will test the following hypotheses:

$$H_0: \pi = 0.3$$

$$H_A: \pi > 0.3,$$

where  $\pi$  is the true response rate, using a one-sided Binomial exact test. A total of n=19 patients will be enrolled and if T=9 or more patients have a response, then the treatment combination will be considered promising; otherwise the treatment combination is not promising. Additionally, the response rate will be summarized using a 90% confidence interval obtained using Jeffrey's prior method.

**Replacement:** Patients that withdraw from the study prior to completing the first cycle of treatment due to toxicity, disease progression, or other treatment related reasons will be considered as 'non-responders' and included in the primary analysis.

Patients that withdraw from the study prior to completing the first cycle of treatment due to non-treatment related reasons will be considered 'unevaluable' for the primary outcome and will be replaced.

**Efficacy Analysis:** Responses to treatment will be measured by serum immunoglobulins, serum free kappa and lambda light chains, serum protein electrophoresis/immunofixation electrophoresis, and 24-hour urine protein electrophoresis/immunofixation. International uniform response criteria will be used. The anti-myeloma activity will be evaluated on an exploratory basis

Roswell Park Protocol No.: I 47217

and will be summarized using descriptive statistics or graphical methods. No formal comparison will be carried forth

### **19.5. Secondary Analyses**

The secondary objectives include: 1) assessment of the abatacept + ixazomib + dexamethasone toxicity profile; 2) assessment of progression-free and overall survival.

The adverse events and drug related toxicities will be summarized by grade using frequencies and relative frequencies. The rate of grade 3 or higher toxicities that are probably or definitely related to abatacept will be reported with 90% confidence intervals obtained using Jeffrey's prior method.

Progression-free and overall survival will be summarized using standard Kaplan-Meier methods; where estimates of median survival and survival rates will be obtained with 90% confidence intervals

**Safety Analysis:** The NCI Common Terminology Criteria for adverse events (CTCAEv5.0) will be used to evaluate toxicity. We will consider a toxicity to be an adverse event that is possibly, probably or definitely related to treatment. The maximum grade of toxicity for each category of interest will be recorded for each patient and the summary results will be tabulated by category and grade. Regimen limiting toxicities (RLT) include any Grade 3 or greater toxicity probably or definitely related to abatacept. The rate of grade 3 or higher toxicities that are probably or definitely related to abatacept will be reported with 90% confidence intervals obtained using Jeffrey's prior method.

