### 1.2. Secondary Objectives

- To assess the toxicity profile of abatacept + ixazomib + dexamethasone in multiple myeloma patients who have relapsed (or who are primary refractory) following treatment with their first proteasome inhibitor-containing regimen (excluding ixazomib), compared to historical controls of ixazomib + dexamethasone.
- To assess progression-free and overall survival profile of abatacept + ixazomib + dexamethasone in multiple myeloma patients who have relapsed (or who are primary refractory) following treatment with their first proteasome inhibitor-containing regimen (excluding ixazomib), compared to historical controls of ixazomib + dexamethasone.

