## **13. RISKS TO SUBJECTS**

Although abatacept has been approved by the FDA for the treatment of rheumatoid arthritis, it has not been given to patients with multiple myeloma (other than the single patient described in Section 2.1 and Figure 2). Because abatacept has never been combined with standard chemotherapy before, there is a risk that there may be additional side effects that arise from the combination. What these side effects will be is unknown but may reflect increased side effects from the ixazomib + dexamethasone chemotherapy combination: these include tumor lysis syndrome (TLS), decreased blood counts, increased blood sugar, hypertension, diarrhea, and nerve damage. In addition, since abatacept, ixa, and dex are immunosuppressive, patients may be at additional risk for infection; however, we do not anticipate that the combination of abatacept + ixazomib + dexamethasone to generate unique side effects that are not already reported for the single agents.

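### Section 19.5 gives an interval only to abatacept-attributed Grade 3+ toxicity; the three-drug regimen's toxicity is tabulated with no interval and no committed per-patient Grade 3+ rate

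*Combined protocol and SAP*

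**What the plan says.** Section 1.2 sets the objective: "To assess the toxicity profile of abatacept + ixazomib + dexamethasone in multiple myeloma patients", and adds that this is to be "compared to historical controls of ixazomib + dexamethasone". Section 19.5 restates it as "assessment of the abatacept + ixazomib + dexamethasone toxicity profile", without the comparator.

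Section 19.5 then plans two kinds of output.

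- Descriptive tables: "The adverse events and drug related toxicities will be summarized by grade using frequencies and relative frequencies". Their scope is the whole treatment: "We will consider a toxicity to be an adverse event that is possibly, probably or definitely related to treatment". Each patient's maximum grade is recorded within each category of interest and tabulated by category and grade. No interval is planned for these.
- One rate with a 90% Jeffreys interval, stated twice: "The rate of grade 3 or higher toxicities that are probably or definitely related to abatacept will be reported with 90% confidence intervals". The matching definition reads "Regimen limiting toxicities (RLT) include any Grade 3 or greater toxicity probably or definitely related to abatacept".

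Section 13 says the combination's additional side effects are unknown but "may reflect increased side effects from the ixazomib + dexamethasone chemotherapy combination". It also names added infection risk.

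**The concern.** The objective is about a regimen, but the only toxicity rate reported with its uncertainty is about one of the regimen's three drugs. With a single arm and all drugs given together, assigning an event to one drug is a judgement that the data cannot check. If abatacept makes ixazomib or dexamethasone toxicity worse, which Section 13 raises as a possibility, an investigator may reasonably assign those events to the partner drugs. The rate with an interval could then look low while the regimen is poorly tolerated. A rate attributed to one drug also cannot be set beside a rate for a historical two-drug regimen.

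**Working it through.** The plan states no toxicity rate, benchmark or interval width, so there is no figure of its own on this point to reproduce. The check has three parts.

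**1. What each section attributes toxicity to**

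| Place | Attributed to |
|---|---|
| 1.2, objective | Three-drug combination |
| 10.3 and 19.3, DLT criteria | All three drugs together |
| 10.2 and 19.3, lead-in rule | Drug-related, no single drug named |
| 19.8, chronic toxicity | Treatment, using the DLT criteria |
| 19.5, tables | Treatment |
| 19.5, RLT and the interval | Abatacept alone |
| 17.3.1, causality scale | Study drug, one scale |

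The RLT definition and the interval are the exception.

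Under 17.3.1, both Probable and Definite require that the event fits a known pattern for the drug and is not reasonably explained by, among other things, other treatment or concomitant drugs. Section 13.2 lists thrombocytopenia, neutropenia, diarrhea and peripheral neuropathy as frequent with ixazomib. The abatacept lists in 13.1 contain none of these four. Applied to abatacept, the scale therefore gives an investigator grounds to score such events below Probable. Events with that score leave the rate that has an interval.

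**2. Size of the possible gap**

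Method: 90% Jeffreys limits are the 5% and 95% quantiles of Beta(x + 0.5, n − x + 0.5), with the lower limit set to 0 at x = 0. n = 19 comes from Section 19.4. The counts x are assumptions.

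Suppose 8 of 19 patients have a Grade 3+ regimen-related toxicity: Beta(8.5, 11.5), 8/19 = 0.421, interval 0.252 to 0.607. The planned rate then depends on how many of the 8 are scored probably or definitely related to abatacept:

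| Attributed to abatacept | Rate | 90% Jeffreys interval |
|---|---|---|
| 0 | 0.000 | 0.000 to 0.095 |
| 2 | 0.105 | 0.031 to 0.262 |
| 4 | 0.211 | 0.092 to 0.390 |
| 8 | 0.421 | 0.252 to 0.607 |

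The same 8 patients can produce any of these lines.

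**3. Whether the category tables fill the gap**

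A patient can appear in several categories, so category counts do not add up to patients. Suppose two categories each show 4 of 19 patients with a Grade 3+ toxicity, and no other category shows any. If the same 4 patients are in both, the per-patient count is 4 (0.211, interval 0.092 to 0.390). If no patient is in both, it is 4 + 4 = 8 (0.421, interval 0.252 to 0.607). The tables alone do not say which.

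**The case against.** The strongest reply is that Section 19.5 does describe the combination. Its opening sentence on toxicity covers all adverse events and drug-related toxicities by grade, and its definition of toxicity is relation to treatment. A reader might infer from the single interval that the combination's toxicity is not estimated at all. The documents do not support that: relative frequencies are planned. What they lack is an interval and a committed line counting patients with any Grade 3+ event. The opening sentence does not say whether it counts patients or events. If a per-patient count were reported, a reader could compute the interval.

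A reader might also infer that the trial's safety decisions rest on attribution to abatacept. They do not. The lead-in rule, the DLT criteria and the Section 19.8 monitoring are not tied to abatacept, and amplified partner-drug toxicity can trigger them. No action in the documents depends on the RLT rate. These rules do not replace the missing estimate, however. Section 10.3 exempts several Grade 3 and 4 events, including anemia, Grade 3 neuropathy and some thrombocytopenia, and Section 19.8 is a suspension rule.

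Section 13 raises amplified partner-drug effects as a possibility and does not predict them. That events would be assigned to the partner drugs is likewise a risk created by the definitions, not a certainty.

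Finally, an abatacept-specific rate is a defensible quantity, because abatacept is the added drug used off-label (Section 32). That is a reason to keep it as a supportive rate. It does not make it the measure of the combination.

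**Conclusion.** The point holds as a mismatch between objective and analysis, and it should be corrected. The combination's toxicity is summarised without an interval and without a committed per-patient Grade 3+ rate. The only interval, and the definition labelled as regimen limiting, belong to an abatacept-attributed subset whose attribution rule is not set out.

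The size is unknown. On the assumed counts of 8 and 2 of 19, the rate with an interval is 11% (3% to 26%) while the regimen's rate is 42% (25% to 61%). These counts only illustrate. The denominator is also an assumption: Section 19 keeps all who receive or attempt treatment, and Section 19.4 replaces some early withdrawals, so the treated number may differ from 19.

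The comparison with ixazomib + dexamethasone is a separate gap. A reader might infer that a regimen-level rate would complete it. It would not, because the documents give no historical toxicity rate and no method of comparison; the historical source is cited for response. The primary endpoint is not affected.

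**What to change.** In Section 19.5:

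1. Report, with 90% Jeffreys intervals over all treated patients, the proportion with at least one Grade 3+ adverse event (a) regardless of attribution and (b) possibly, probably or definitely related to the regimen, which is the plan's own definition of toxicity.
2. Define RLT by relation to the regimen, or relabel it as abatacept-attributed toxicity.
3. Keep the abatacept-attributed rate as supportive, and state in 17.3.1 how relation to abatacept is recorded separately from relation to the regimen.
4. For the historical comparison, either state a sourced Grade 3+ rate for ixazomib + dexamethasone and compare descriptively, or delete the comparison from the toxicity objective in 1.2. If it is kept, note that 17.1.3 records laboratory abnormalities as adverse events only when clinically significant and needing active management, which may limit comparability.

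The cost is two table lines and short text edits. For (a), Section 17.3.2 already requires Grade 3 and 4 events at every attribution level, and deaths are captured as SAEs under 17.4. For (b), relation to the regimen must be recorded, as the existing tables already assume. The new rates can only equal or exceed the abatacept-attributed one, so the reported toxicity may look less favourable.

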### **19.6. Exploratory Analyses**

Exploratory analyses will determine whether myeloma expression of CD28, CD86 serum kynurenone, IL-6 levels influences the clinical outcomes.

The CD28, CD86 expression, serum kynurenone and IL-6 levels will be summarized in the overall sample and by response status using the mean, standard deviation, and percentiles. The association between CD28, CD86, serum kynurenone and IL-6 expression/levels and response will be evaluated using logistic regression models; while the association with the survival outcomes will be evaluated using Cox regression models. Odds and hazard ratios, with corresponding 90% confidence intervals, will be obtained from model estimates.

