### 11.9.1. Blood Sample Collection

Blood samples will be collected via venipuncture for serum kynurenine and IL-6 assays. Samples will be collected using five (5), 3.5 mL gold top SST collection tubes.

Samples for analysis will be obtained on:

- Baseline
- Cycle 2 Day 1 and on Day 1 of every subsequent 28-day cycle
- End of Treatment
- Post-Treatment Follow-Up

Correlative samples will be drawn at the same time as the other scheduled standard of care lab tests. Collection tubes are to be labeled with the participant's MR number, participant's initials, participant's study number, clinical study number, time of collection, and protocol day. Samples will be sent at room temperature to the attention of Laboratory Medicine – Protocol Clinical Research Support (pneumatic Station 19) where they will get accessioned for tracking in the source document. Once sample receipt has been documented, the samples will be sent at ambient temperature to pneumatic Station 86 (located in [name]) to the DBBR lab. The DBBR laboratory will be notified via telephone *and* email (see contact information below) prior to sample shipment and, the samples will be held in CSPO until a response is received acknowledging that personnel are available to procure the samples from the pneumatic tube station. Samples will be processed in DBBR and will be immediately frozen at -80°C or below until analyzed. Additional sample that may remain once the analysis is complete will be stored for future use in DBBR (see Section 15).

Roswell Park Comprehensive Cancer Center  
DBBR Laboratory  
[name] via Tube station # 86  
Attn: Study Number – I 47217  
[name]  
[name]  
[contact]  
[contact]  
[[contact]](mailto:[contact])

\*Please notify [name] and [name] (via phone or email calendar invitation). Please include all the relevant information in the calendar invite and the email e.g. Study Name, Protocol #, MRN, Initials, timepoint / collection information. This should be done for all blood sample collections.

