## **19. STATISTICAL PLAN**

This is a single-arm, open-label, Phase II study of abatacept + ixazomib + dexamethasone in relapsed, multiple myeloma patients.

Summary statistics for continuous variables will include the mean, standard deviation, percentiles and range (minimum/maximum). Categorical variables will be presented as frequencies and relative frequencies; and time-to-event variables will be summarized using Kaplan-Meier methods.

The analyses will be conducted using the intent-to-treat principle, where all patients who receive or attempt to receive treatment are included. All analyses will be conducted in SAS v9.4 (Cary, NC) at a significance level of 0.1.

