### **19.1. Sample Size Determination**

The sample size determination is based on the primary analysis of response rate. Prior studies have demonstrated a second-line treatment response rate of approximately 30% in this patient population (34), and we would consider a response rate for the proposed treatment combination (abatacept + ixazomib + dexamethasone) of 50-60% to be a clinically relevant improvement. Therefore, we will test the following hypotheses:

$$H_0: \pi = 0.3$$

$$H_A: \pi > 0.3$$

where  $\pi$  is the true response rate, using a one-sided Binomial exact test. If the true response rate for the proposed treatment combination is 60%, then our study design ( $n=19$ ) as a 90% chance of achieving statistical significance at  $\alpha = 0.1$ .

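### With at most 19 patients, the biomarker models in Section 19.6 need a small-sample estimator and a named (baseline) marker value

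*Combined protocol and SAP*

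**What the plan says.** Section 19.6 covers four markers: CD28 and CD86 expression on myeloma cells, and serum kynurenine and IL-6. It says that marker "expression/levels and response will be evaluated using logistic regression models; while the association with the survival outcomes will be evaluated using Cox regression models". Effect estimates (odds ratios and hazard ratios) are to be reported with 90% intervals taken from the models. The section names no penalised or exact method, does not say how many markers enter a model, and does not say which measurement of a marker is used.

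The sample is small. Section 19.4 says: "A total of n=19 patients will be enrolled and if T=9 or more patients have a response", the combination is judged promising. Section 19 sets all analyses "at a significance level of 0.1".

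Serum is sampled repeatedly. Section 11.9.1 lists baseline, then "Cycle 2 Day 1 and on Day 1 of every subsequent 28-day cycle", then end of treatment and post-treatment follow-up. Section 8.3 gives no time point for the serum markers. It places CD28 and CD86 at enrolment and at progression or off study. Under Section 11.2 an earlier marrow can stand in for a fresh baseline sample if positivity is already established.

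**The concern.** Two details are left open, and each affects how a marker result would be read.

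The first is the estimator. Maximum-likelihood logistic regression is biased away from 1 in small samples when the true association is not null, and its estimates are very variable. With about 6 to 11 responders among 19 patients, a moderate association would tend to be reported as larger than it is.

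The second is timing. From Cycle 2, serum is drawn at the same Day 1 visits as the disease status evaluation (Section 11.3). Section 2.1 says myeloma CD28 drives dendritic-cell IL-6 and the enzyme that produces kynurenine, so on-treatment levels may fall because the tumour has shrunk. Used as a fixed predictor, such a value may follow the outcome it is meant to explain. In a Cox model it also uses information from after time zero. The end-of-treatment marrow has the same difficulty, because Section 11.9.2 times it by complete response, progression or leaving the study.

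These markers are the trial's mechanistic rationale, and CD28 or CD86 positivity is an entry criterion. A reader may therefore give the exploratory results some weight.

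**Working it through.** **The plan's own figure.** Section 19.6 gives no operating characteristic. The one stated design figure is in Section 19.1: "If the true response rate for the proposed treatment combination is 60"%, the design has a "90% chance of achieving statistical significance at" level 0.1, "using a one-sided Binomial exact test". With X binomial and n = 19:

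- P(X ≥ 9 | 0.30) = 0.084, and P(X ≥ 8 | 0.30) = 0.182, so 9 is the smallest cut-off within 0.1.
- P(X ≥ 9 | 0.60) = 0.912, which agrees with the stated 90%.

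**Size of the response groups.** The 30% is the plan's null rate (Section 19.4) and the 60% its alternative (Section 19.1).

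- At 30%: 19 × 0.30 = 5.7 responders.
- At 60%: 19 × 0.60 = 11.4 responders and 7.6 non-responders.

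The rarer outcome group therefore has about 6 to 8 patients.

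**Estimator.** The documents give no marker effect or distribution, so the following are assumptions: one standard normal marker per model; true odds ratio (OR) of 1, 2 or 3 per SD; n = 19; 3,000 simulated trials per setting. Maximum likelihood maximises l(β). Firth's method maximises l(β) + ½ log|I(β)|, where I is the information matrix. The average OR is exp(mean log OR) over fits that converged.

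| Response rate | True OR | ML average | ML median | Firth average | Firth median | ML fit failed |
|---|---|---|---|---|---|---|
| 30% | 1 | 0.99 | 1.00 | 0.99 | 1.00 | 0.5% |
| 30% | 2 | 2.53 | 2.17 | 2.07 | 1.88 | 1.1% |
| 30% | 3 | 4.54 | 3.48 | 3.11 | 2.71 | 1.7% |
| 60% | 1 | 1.00 | 1.00 | 1.01 | 1.00 | 0.1% |
| 60% | 2 | 2.45 | 2.16 | 2.01 | 1.88 | 0.1% |
| 60% | 3 | 4.28 | 3.33 | 3.06 | 2.65 | 0.8% |

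Across repeat simulations at a true OR of 2, the maximum-likelihood average lay between 2.3 and 2.6, the median between 2.0 and 2.2, and the Firth average between 1.9 and 2.1. The root mean squared error of the log OR fell from 0.85-1.03 to 0.60-0.69: 1 − 0.60/0.85 = 0.29 and 1 − 0.69/1.03 = 0.33, or about 30%.

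At a true OR of 1, the ordinary Wald test at the 90% level rejected in 7-8% of one-marker trials, so small-sample bias does not raise the false-positive rate. Coverage of the ordinary 90% interval was 92-95% over the settings in the table.

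**Timing.** Assumptions: response rate 50%; a marker with no predictive value; response itself lowers the later level by d SD. The share of trials flagging the marker at the 90% level is:

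- d = 0: 8%
- d = 0.5: 25%
- d = 1: 58%

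The d = 0 row also describes the baseline value, which response cannot have moved. These rates apply only if a post-baseline level is modelled as a fixed predictor, and the size of the shift is assumed.

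**The case against.** The strongest reply is that this is a labelled exploratory analysis that reports estimates with 90% intervals, that those intervals already show the imprecision, and that no decision depends on it. Most of that stands. Ordinary intervals cover at or above their nominal level in the simulations, and the primary test, the safety lead-in and the chronic-toxicity rule do not use the markers. This limits the importance of the point, but it does not remove the gain in accuracy from a better estimator or the need to name the sample.

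It can also be said that the average overstates the problem, because a long upper tail pulls it up. That is fair: for a true OR of 2 the one-marker median is only 2.0-2.2. The larger gain from Firth is in stability.

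On timing, the exploratory objective in Section 1.2 asks only whether markers are correlated with outcomes, and a change in IL-6 that accompanies response is a legitimate correlative question. That stands too. However, Section 19.6 then asks whether markers influence outcomes, and it does not separate the two questions.

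A reader might infer more than the documents support:

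- That small-sample bias could create an association where none exists. It does not: at a true OR of 1 the average estimate is 1.
- That all four markers will enter one model, where bias and separation would be worse. No section plans such a model.
- That the plan intends to use post-treatment levels as predictors. It does not say so; a baseline draw is scheduled, and the choice is simply left open.
- That many markers and outcomes at level 0.1 give a calculable high chance of a false finding. The tests are not independent, and Section 19.6 attaches no decision rule to any marker.

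**Conclusion.** The point holds as an inexpensive improvement. Section 19.6 leaves standard logistic regression as the natural reading; this is inferred from the absence of any named alternative. With 19 patients, that estimator exaggerates real associations on average and is noticeably less accurate than Firth's. For one normal marker with a true OR of 2 per SD, the average is about 2.3-2.6 against 1.9-2.1, and Firth's root mean squared error on the log scale is about 30% smaller. There is no bias at an OR of 1. The effect size and marker distribution are assumptions, so these figures are illustrations and not predictions for this trial.

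The missing time point is a separate omission. It does harm only if a post-baseline value is used as a fixed predictor. Naming the baseline value removes that risk. Severity is low: the analysis is exploratory and the primary conclusion does not depend on it.

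**What to change.** Add to Section 19.6:

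1. The predictor is the baseline, pre-dose value of each marker. For CD28 and CD86, record the date of the marrow used, since an earlier sample is allowed.
2. Fit one marker per model, using Firth-penalised logistic regression for response and Firth-penalised Cox regression where events are few, with profile-likelihood 90% intervals.
3. Use later values only as time-dependent covariates in Cox models, or in a landmark analysis that excludes patients whose outcome has already occurred by the landmark. Cycle 2 Day 1 needs particular care, because it is also the first post-baseline disease evaluation (Section 11.3). Section 16 requires two consecutive assessments for response, so the rule should state which of them dates it.

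The cost is SAP wording and a model option in the planned software, with no added patients, visits or assays. The downside is that Firth estimates are shrunk towards 1 and look less striking; the median in the simulations was 1.88 for a true OR of 2. Standard errors did not increase: one-marker values were 0.52-0.61 with Firth against 0.53-0.65 without.
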